#### D.7.3 Data Management

The data coordinating center (DCC) will be established in Chicago, where the study statistician and statistical programmers are housed. [name] has significant experience supervising DCCs. He has maintained large data repositories on international collaborative studies at Loyola for over 10 years. He also was the director of the DCC for the Chicago Initiative to Raise Asthma Health Equity for which he was in charge of maintaining a database of asthma screening on over 50,000 children from the Chicago Public Schools. Data entry will be the responsibility of each site coordinator. Data will be sent to the DCC along with copies of the paper forms used to collect them for storage, editing, cleaning, and preparation for publication. Data quality and assurance processes will be implemented and kept in place for the duration of the study. All data files will be stripped from personal identifiers to ensure participant confidentiality. Data backups will be performed regularly following the guidelines of the Department of Preventive Medicine IT.

#### D.7.4 Missing Data

Briefly, missing data will be handled statistically by using mixed effects models, which will (1) allow use of all data even if some time points are missing, (2) accommodate subject measurements that were not obtained at the precise time, (3) use growth curve models, which is a special case of mixed effects models, which again permits use of the full data set despite missing values and (4) allow for correlations of variables within a participant. The mixed models approach assumes that the data is missing at random (MAR) and, as such, will not bias the analysis. However, if it is determined that the data may not be randomly missing and thus non-ignorable, then two well accepted approaches to handle this situation will be implemented, namely selection models [196, 197] and pattern mixture models [198-201]. Selection models comprise to steps. In the first, a predictive model for drop-out (missingness) is developed as a function of variables measured prior to dropout (e.g. baseline information). Thus, the probability (propensity) of missingness is estimated for each participant.

Then, in the second step, the propensity score is entered into the regression model as a covariate to adjust for the effect of drop-outs. We will also apply mixed-effect selection models to account for non-ignorable missing data [200]. In *pattern-mixture models* we first group the data according to a missing pattern. For instance, in a study with 3 time point determinations there will be total of 8 ( $2^3$ ) missing data patterns (e.g. OOO, OOM, OMM, OMO, where O stands for observed and M for missing). Then, a mixed-effects model is fit to the data with the same covariates as the original mixed-effects model, in addition to a grouping variable representing the missing data patterns to account for drop-out. Formally, dummy variables are created to represent each of the data patterns. The final model includes all the covariates, the dummy variables and interactions of these dummy variables with other variables in the model. This approach allows determination of i) the degree of dependence of the outcome variable on the missing data patterns; ii) the extent of the influence of the missing data patterns on the association between other variables and outcome (effect modification). Overall estimates of the association between a given variable and outcome can be estimated by averaging over all missing data patterns.

## D.8 Limitations

This study is based on the premise that objective measurement of EE will be required to fully understand the causes of the on-going secular trends in obesity. Given prior research on the role of specific sedentary activities, it is reasonable to test the hypothesis that AEE will vary across the social settings we have chosen to study. The value of our study will be in quantifying the overall magnitude of this difference and its within-site relationship. We recognize that it is possible that increases in energy intake—rather than expenditure—could be the determining, or even sole factor, in weight gain and diabetes risk; demonstrating the absence of a PA-obesity relationship will directly support this alternative hypothesis. We will capture data on EI from questionnaires as well, although we recognize its limitations.

On the other hand, the net positive energy balance required to cause gradual weight gain can be quite subtle (in the range of 20-40 kcal/d for adults). Given that this net excess is likely to be due to a combination of both decreased AEE and increased caloric intake, the contrast in population means for AEE could be hard to define. As in all such etiologic studies, therefore, we run the risk of a false negative due to low power. This result, however, would not be uninformative since it would be important to know that large mean shifts in AEE were not driving this epidemic. At the same time, a wide distribution of AEE levels can be anticipated among participants within each site, and we anticipate finding important relationships in the individual-level analyses. The entire success of the project, therefore, does not rest on the group comparisons.

The focus of this study is on the net outcome of a complex regulatory system in natural populations. The class of effects that include the interaction of socially-embedded behavior, food patterns, cultural norms, required and voluntary PA, etc., can only be examined in observational studies. Controlled experiments are therefore not useful to address this question. Long-term prospective studies have clear advantages over cross-sectional and short-term studies; however, they are also difficult to conduct and do not fit within the NIH funding framework. In most instances where epidemiologic research has tried to define risk for chronic disease, cross-sectional studies have effectively summarized the cumulative effect of prior exposures and have consistently identified true relationships among CVD risk factors (e.g., BMI vs. BP, glucose, and cholesterol). Clearly, studies of much longer duration are ultimately necessary to support causal inferences and will be needed in the future.

This project involves recruitment in 5 countries, collection of a complex set of data, and follow-up for two years. The methods must be rigorously standardized to ensure comparability. We recognize the challenge posed by these aspects of the study. We have many years of experience in cross-cultural research and have implemented standardized data collection protocols for similar complex surveys. Our study of the African diaspora was both the largest international collaborative study ever conducted on hypertension and the only one that has yielded standardized cross-cultural prevalence estimates [81, 202]. We regard project described in this application as a major research opportunity which could have long-term significance. It will be the sole research focus of the PI who has invested more than 6 years bringing this project to maturity. We are therefore committed to a maximal effort at study management and are convinced that we can obtain complete high quality data from all the study sites.

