- 3) Population mean levels of AEE are negatively related to population mean levels of obesity/relative weight.
- 4) Adipocytokines (e.g., adiponectin and leptin) and hormones (e.g., ghrelin) influence weight regulation and insulin sensitivity and interact with AEE.
- 5) Heavy metals, such as arsenic, mercury, lead and cadmium, are positively associated with obesity and markers of diabetes and CVD risk.
- 6) Human gut and oral microbiome and plasma metabolites are associated with obesity through short chain fatty acids, a byproduct of gut fermentation of complex carbohydrates and is mediated by lifestyle and geographic location.

*To test these hypotheses we will complete the following Specific Aims:*

- 1) Recruit 500 participants, ages 25-45, from each of 5 populations (total N = 2,500); measure AEE with accelerometry; collect 24-hour dietary recalls; assess fasting glucose/insulin, ghrelin, and adipocytokines (adiponectin, leptin).
- 2) Measure AEE using DLW in a random subset of 75 participants from each of the 5 populations at baseline (total n = 375).
- 3) Repeat AEE measurement with accelerometry on all participants at 24 months; repeat weight at 12 and 24 months and body composition at 24 months.
- 4) Examine the relationship between AEE and body composition within and among populations at baseline and at follow-up; assess inter-relations of AEE and diet, glucose, insulin, ghrelin and adipocytokines.
- 5) Measure serum 25(OH)D and intact parathyroid hormone (iPTH) levels in 500 adults from the 5 METS sites (total N=2,500) at baseline and determine associations with latitude, diet, physical activity, adiposity, blood pressure (BP), and biochemical risk factors for CVD (eg, insulin, glucose, adiponectin, leptin, cholesterol).
- 6) Examine the association between baseline serum 25(OH)D and iPTH levels and changes in body composition and blood pressure over 6.5 years of follow-up.
- 7) Repeat measurement of serum 25(OH)D and iPTH at third follow-up examination (approximately 3.5 years after baseline) and measure BMD using DXA in the available cohort.
- 8) Identify a metabolite profile that predicts progression to IGT/T2D in diverse black populations spanning the epidemiologic transition.
- 9) We hypothesize that the plasma metabolite profile at baseline (2009) will be significantly associated with changes in diabetic status over the same 6-year period (2009 to 2015), i.e. normal glucose tolerance (NGT) to IGT and/or T2D.  

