## B.9 Summary

Although the “obesity epidemic” has received enormous attention in recent years, the mechanisms through which the energy budget is being perturbed are still not well understood. In particular, the role of declining AEE as a causal mechanism in population-wide increases in relative weight deserves much greater attention. Despite widespread perception that variation in normal activity levels (as opposed to voluntary increases in high-intensity activity, as typical of trials) is correlated with change in weight, the data do not support this conclusion. Research in this vital area has been handicapped by lack of access to precise objective methods of measurement. A new generation of epidemiologic research will be required before we can base causal inferences or public health recommendations on something more than assumptions. As with other chronic CVD, international comparisons could be particularly informative.

The test of our study hypothesis will be “two-sided”. That is to say, the presence or absence of an association can be given a clear interpretation. Of course, given the body of evidence that increased AEE has health advantages, absence of an association would not be taken to suggest that AEE is of no value. Rather, the correct interpretation would be that declining AEE is unlikely to be the driving force behind the rise in obesity, nor will modest increases in AEE be adequate to reverse the trends.

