Although the study is not powered to test for differences in the association across sites (i.e., effect modification), we will undertake this task to ensure that large differences among the correlation coefficients do not exist. In addition, sites in which the correlation coefficient is deemed to be similar will be combined, and then comparisons of the correlations will be performed. For the sake of illustration, assume that 2 sites ( $n = 150$  individuals) are compared to other 2 sites ( $n = 150$  individuals). Thus, a two-sample, one-sided test of the correlations, assuming -0.4 versus -0.65, will yield over 91% power, whereas the power will be over 80% for comparison of -0.45 and -0.65, and between -0.35 and -0.6 the power is greater than 85%. Combining the data samples from all 5 sites and assuming constant

association will demonstrate a correlation between AEE and change in body composition of -0.15 or smaller (larger in absolute value) with over 83% power.

3) Mean levels of AEE are negatively related to mean levels of obesity/relative weight among the populations.

As previously demonstrated, sample sizes within sites will allow us to rule out correlations larger than 0.33 (absolute value), even when AEE is determined by DLW. Furthermore, we have estimated (cf. Preliminary Studies) that the within-site correlation between AEE and body composition of individual data could be as large as 0.6. We anticipate that the correlation between mean AEE levels and mean body composition will exceed 0.85. This estimate is justified in the following manner. A Fisher's Z-transformation 5%-significance test will have over 55% power to detect this correlation with 5 values corresponding to the 5 sites of the study. However, after dividing our samples by gender there will be 10 observations (2 X 5 countries), resulting in over 95% statistical power. Assuming an effective sample size of 7, to account for within-country correlations, the statistical power is 80%. Note that additional power will be gained when weighted linear regression methods are applied to estimate the correlation (slope) between AEE and body composition using meta-regression. Given the strong a prior hypothesis we can also compare mean AEE in the groups with the highest and lowest rates of obesity to test the ecological association.

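### D.8 reads a low-power null on the population-level hypothesis as evidence that AEE shifts are not driving obesity, but with five populations most non-significant results remain compatible with the expected correlation of -0.85

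*Combined protocol and SAP*

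**What the plan says.** Hypothesis 3 (section A) is that "Population mean levels of AEE are negatively related to population mean levels of obesity/relative weight". The power section (D.7.2, item 3) states: "We anticipate that the correlation between mean AEE levels and mean body composition will exceed 0.85". It continues: "A Fisher's Z-transformation 5%-significance test will have over 55% power to detect this correlation with 5 values corresponding to the 5 sites of the study". For sex-by-site means it says that "after dividing our samples by gender there will be 10 observations (2 X 5 countries), resulting in over 95% statistical power", and it gives 80% at an effective sample size of 7, which allows for correlation within countries.

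D.8 notes that the daily energy surplus behind gradual weight gain is small (20 to 40 kcal/d). Contrasts in mean AEE may therefore be hard to establish, and the study could return a falsely negative answer for want of power. It goes on to say that such a result would still be informative, since "it would be important to know that large mean shifts in AEE were not driving this epidemic". B.9, writing about the study hypothesis as a whole, says that absence of an association should be interpreted to mean that "declining AEE is unlikely to be the driving force behind the rise in obesity".

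For a null result on Hypothesis 3, the plan gives no confidence interval, no margin and no smallest correlation to be ruled out.

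**The concern.** The D.8 reasoning contradicts itself. A false negative is a real association that the data failed to show, so it cannot count as evidence that the association is absent. A non-significant result can support a negative conclusion only if its interval excludes associations large enough to matter, and the plan names no such value.

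At stake is what the study may say about one of its main questions. An inconclusive five-point comparison could be reported as evidence against AEE as a population-level cause of obesity, although the data would still fit the strong association that the plan predicts. Section B.1 places AEE recommendations at the core of current public health policy, so the distinction matters.

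**Working it through.** **Inputs (D.7.2, item 3).** Expected correlation 0.85 in absolute value, negative under Hypothesis 3; 5% Fisher Z test; n = 5 sites, n = 10 sex-by-site means, or effective n = 7. The sidedness of this test is not stated. Item 1 of the same section uses a one-sided Fisher Z test.

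**Step 1: reproduce the plan's power.** Power = Φ(atanh(0.85)·√(n−3) − z), with atanh(0.85) = 1.256.

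| n | Plan | One-sided (z = 1.645) | Two-sided (z = 1.960) |
|---|---|---|---|
| 5 | over 55% | 55.2% | 42.7% |
| 7 | 80% | 80.7% | 71.0% |
| 10 | over 95% | 95.3% | 91.4% |

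Only the one-sided test reproduces all three figures. The miss rate at a true r of -0.85 is then 100 − 55.2 = about 45% at n = 5 and 100 − 80.7 = about 19% at n = 7. The formula is approximate at such small n. Simulated bivariate normal data give misses of about 34% and 13% for the same one-sided test.

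**Step 2: which results are non-significant, and which exclude -0.85?** A result is non-significant when the observed r is weaker than −tanh(z/√(n−3)). It excludes -0.85 when the observed r is above tanh(−1.256 + z/√(n−3)).

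| n | Basis | Non-significant if r is above | Excludes -0.85 if r is above |
|---|---|---|---|
| 5 | one-sided | -0.82 | -0.09 |
| 5 | two-sided | -0.88 | +0.13 |
| 7 | one-sided | -0.68 | -0.41 |
| 7 | two-sided | -0.75 | -0.27 |
| 10 | one-sided | -0.55 | -0.56 |
| 10 | two-sided | -0.63 | -0.47 |

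At n = 5, an observed r anywhere between -0.82 and -0.09 (one-sided), or between -0.88 and +0.13 (two-sided), is both non-significant and compatible with -0.85. For example, an observed r of -0.5 has a two-sided interval of -0.96 to +0.68.

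**Step 3: an observed correlation of exactly zero.** At n = 5 the Fisher Z lower limit is tanh(−1.960/√2) = -0.88 two-sided and tanh(−1.645/√2) = -0.82 one-sided. The exact two-sided limit under bivariate normality is -0.81. So -0.85 is inside the first limit and outside the other two. At n = 7 and n = 10 the two-sided Fisher Z limits are -0.75 and -0.63, so an observed zero excludes -0.85.

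**Step 4: how often does a null mislead if the plan's expectation is right?** In simulated bivariate normal data with a true r of -0.85, the share of non-significant results whose Fisher Z limit still includes -0.85 is 94% (one-sided) to 98% (two-sided) at n = 5, and 78% to 93% at n = 7. At n = 10 it is none one-sided and 73% two-sided, but that count treats the two sexes in a country as independent, which the plan itself discounts by moving to 7.

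**The case against.** The strongest defence is that D.8 speaks of large shifts in mean AEE, and that the difficulty it names is detecting small ones. Site means will be precise. As an illustration, take the sex-specific pilot SDs in Table 1 (230 to 566 kcal/d) and 500 participants per site, with sampling error only. The 95% half-width for a difference between two sites is 1.96·SD·√(2/500), or about 29 to 70 kcal/d. D.7.1.3 plans two-sample comparisons of site means, and D.7.2 allows a comparison of mean AEE between the groups with the highest and lowest obesity. If all sites proved to have similar mean AEE, no five-point correlation would be needed to say so.

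That stands, but only for the existence of large differences. If mean AEE does differ between sites, whether the differences track obesity is judged on five populations, and precise means do not add populations. The pilot means in Table 1 already range from 688 to 1090 kcal/d in men.

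B.9 concerns the study hypothesis as a whole, including person-level analyses in 2,500 people. It is not a decision rule for Hypothesis 3, so only its population-level part is in question. The plan is also candid. D.8 admits low power and says the project does not depend on the group comparisons, and D.7.2 says person-level relationships will be tested first. None of this supplies a bound for reading a null.

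A reader might infer that even an observed correlation of zero could never exclude -0.85. The documents do not support that. It holds only for a two-sided Fisher Z interval at n = 5. It fails on the one-sided basis that reproduces the plan's power, under the exact distribution, and at the plan's counts of 7 or 10.

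**Conclusion.** The concern holds for the population-level null. D.8 draws a negative conclusion from a result it has just described as a possible failure of power, with no bound attached. With five populations, a non-significant result is usually still compatible with the -0.85 the plan expects. By the plan's formula, a true correlation of that size is missed about 45% of the time at n = 5 and 19% at an effective n of 7. An observed zero is borderline at n = 5 and is informative at n = 7 or 10.

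This rests on the plan's Fisher Z framework, on one-sidedness inferred from the reproduced figures, and on approximate normality of the population means. The planned analysis is a weighted meta-regression with energy-intake terms, so its interval will differ. Each added covariate uses a degree of freedom, of which five sites leave few. The documents do not say that a non-significant correlation would by itself trigger the B.9 conclusion; the point is that nothing in the plan prevents that reading.

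**What to change.** In D.8, delete the statement that a false negative from low power would show that large AEE shifts were not the driver. In its place, and for the population-level part of B.9, state that:

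- a non-significant ecological result will be reported with the confidence interval for the between-population slope and correlation from the planned meta-regression, and with the interval for differences in mean AEE between sites;
- a conclusion that AEE differences are not a major driver will be drawn only if the interval excludes a correlation that the sponsor fixes and justifies in advance, for which the plan's own -0.85 is the natural reference;
- otherwise the result will be called inconclusive.

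The sidedness of the interval and the number of units it assumes (5, 7 or 10) should be fixed at the same time, because at n = 5 they decide how an observed zero is read. The cost is wording in two sections and a few reported intervals. The study also gives up a negative ecological conclusion that five populations usually cannot support.

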## **HUMAN SUBJECTS**

### **E.1 Risks to the Subjects**

This study will involve the collection of medical information, activity data, plasma and urine samples from 2,500 human participants, ages 25-45 years, from communities in 5 countries. The participants will be recruited from residential neighborhoods in Igbo-Ora, Nigeria; Cape Town, South Africa; Seychelles; Spanish Town, Jamaica; and Maywood, IL, USA. Participants will be recruited for this study as the primary aim is to determine whether or not differences in energy expenditure are responsible for the differences in relative weight, change in relative weight over time, and diabetes risk between these countries.

#### **E.1.1 Sources of Materials**

Information, activity monitoring data, and plasma samples will be collected from all participants (n = 2,500); urine samples will be collected on a subset participating in the DLW component of the study (n = 375). Demographic, anthropometric, PA, environmental, and lifestyle data will be collected on all participants. They will be assigned an identification number upon enrollment into the study. Linkage of identification number with name, address, birth date or any other identifying information will be kept by the data manager at the respective institutions in a separate, password-protected data file. Only the data managers and study investigators will have access to the linkage file. AEE data, anthropometrics, and specimens will be collected for this study by specifically trained field staff at each of the institutions. Demographic, health history, and questionnaire data will be collected by a one-on-one interview. The participants will be provided with an extensive explanation of the intended study in his/her native language. The data will be coded, cleaned and double entered by trained staff at Loyola.

